## **9.8        Interim Analysis**

No formal interim analysis will be conducted for the study.

## **9.9        Other Topics**

### **9.9.1      *Pharmacokinetics, [REDACTED]***

Serum trough concentrations ( $C_{trough}$ ) of CC-93538 will be summarized with descriptive statistics by treatment and visit. Additional analyses may be conducted as appropriate (eg, by ADA status).

### **9.9.3     *Internal Safety Management Team***

In addition to ongoing safety monitoring conducted by investigators and individual study personnel, cumulative and interval blinded AEs, SAEs, discontinuations due to AEs, and abnormal laboratory findings will be reviewed internally by the Celgene SMT. The SMT is comprised of lead representatives from multiple Celgene functions engaged in the CC-93538 development program. The scope, conduct, processes, and accountabilities are specified by Celgene Standard Operating Procedure (SOP).

### **9.9.4     *External Data Monitoring Committee***

Safety monitoring will also be performed by an external, independent DMC. A DMC will be convened that will be comprised of physician experts with experience in treating subjects with EGE and a statistician, all of whom are not otherwise involved in the study conduct and for whom there is no identified conflict of interest. During the study, the DMC will review selected data (to be specified in the DMC charter) on a regular basis for the assessment of benefit-risk and determination of study continuation. An independent third party will prepare the reports of aggregate data summaries and individual subject data listings, as appropriate, for the DMC members for each scheduled meeting. Operational details for the DMC, including a blinding plan to assure that all personnel involved in the conduct of the study remain blinded to the results of data reviews, will also be described in the DMC charter.

## **10 ADVERSE EVENTS**

### **10.1 Monitoring, Recording and Reporting of Adverse Events**

An AE is any noxious, unintended, or untoward medical occurrence that may appear or worsen in a subject during the course of a study. It may be a new intercurrent illness, a worsening concomitant illness, an injury, or any concomitant impairment of the subject's health, including laboratory test values (as specified by the criteria in [Section 10.3](#)), regardless of etiology. Any worsening (ie, any clinically significant adverse change in the frequency or intensity of a pre-existing condition) should be considered an AE except for symptoms associated with an EGE flare requiring an EGE Flare Assessment, as referenced in [Section 6.4.2.10](#). However, any EGE flare that meets the criteria for seriousness as detailed in [Section 10.2.1](#), should be documented as an SAE in addition to an EGE flare. A diagnosis or syndrome should be recorded on the AE page of the case report form (CRF) rather than the individual signs or symptoms of the diagnosis or syndrome.

Abuse, withdrawal, sensitivity or toxicity to an IP should be reported as an AE. Overdose, accidental or intentional, whether or not it is associated with an AE should be reported on the overdose CRF. (See [Section 7.2](#) for the definition of overdose.) Any sequela of an accidental or intentional overdose of an IP which meets the definition of an adverse event, should be reported as an AE on the CRF. If the sequela of an overdose meets serious criteria, then it must be marked as serious on the CRF. The overdose itself should not be reported as an AE.

In the event of overdose, the subject should be monitored as appropriate and should receive supportive measures as necessary. There is no known specific antidote for CC-93538 overdose. Actual treatment should depend on the severity of the clinical situation and the judgment and experience of the treating physician.

All subjects will be monitored for AEs, including AEs related to SARS-CoV-2 infection, during the study. Assessments may include monitoring of any or all of the following parameters: the subject's clinical symptoms, laboratory, pathological, radiological or surgical findings, physical examination findings, or findings from other tests and/or procedures. In addition, /PFS device failures or malfunctions should be captured during the study, and any device-related AEs should also be documented. Each study visit will include an assessment for AEs, and subjects who develop an intercurrent illness between study visits are encouraged to contact the investigator, who will determine if a clinical assessment is required. In addition, AEs or SAEs related to SARS-CoV-2 infection will also trigger additional data collection through specialized eCRF pages, which will allow the Sponsor to further evaluate these events.

All AEs, including AEs related to SARS-CoV-2 infection, will be recorded by the investigator from the time the subject signs informed consent/assent until 16 weeks after the last dose of IP or the final 16-week Safety Follow-up Visit, whichever is longer, as well as those SAEs made known to the investigator at any time thereafter that are suspected of being related to IP. AEs and SAEs will be recorded on the AE page of the eCRF and in the subject's source documents. Refer to [Section 10.5](#) for instructions on how to report SAE to Drug Safety.

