Overall, 17 of 52 subjects (32.7%) reported at least one TEAE. The majority of TEAEs were mild to moderate in severity. The most frequent TEAEs reported included injection site bruising (2 subjects from each treatment group) and coronavirus disease 2019 (COVID-19) (3 subjects from the 150 mg/mL treatment group and one subject from the 180 mg/mL treatment group). No other TEAEs were reported in more than one patient. Overall, only 2 subjects reported at least one TEAE related to study drug (frequent bowel movements [one subject from the 150 mg/mL treatment group] and injection site pain [one subject from the 180 mg/mL treatment group]). No deaths or SAEs were reported, and no subject had a TEAE that led to early discontinuation from the study. All TEAEs were recovered/resolved by the end of the study.

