**Table 2: Study Endpoints: Induction and Maintenance Phase Endpoints Through Week 48**

Endpoint	Name	Description	Timeframe
Primary	Eosinophil histologic response	Changes in mean number of peak eosinophils (eos) per high-power field (hpf) in gastrointestinal (GI) biopsies from baseline to Week 16	Week 16
Key Secondary	Clinical response: eosinophilic gastroenteritis (EGE) -related symptoms	
Changes from baseline in each of 5 domain scores of the Izumo Scale (APPENDIX B) from baseline
 
 
• Heartburn Symptoms domain
 
• Gastric Pain Symptoms domain
 
• Stomach Heaviness Symptoms domain
 
• Constipation Symptoms domain
 
• Diarrhea Symptoms domain
 
 
Gastric Pain Symptoms domain, Stomach Heaviness Symptoms domain, and Diarrhea Symptoms domain are Symptoms of Interest of EGE
	Weeks 16 and 48
	Clinical and histologic response composite	
The proportion of responders defined as subjects who achieve both clinical and histologic response:
 
 
• Clinical response defined as the proportion of subjects who achieve < 4/15 in each of three Symptoms of Interest (Gastric Pain Symptoms domain, Stomach Heaviness Symptoms domain, and Diarrhea Symptoms domain) scores of the Izumo Scale from baseline
 
• Histologic response defined as a > 75% reduction of peak gastric and/or duodenal eos count from baseline
 
	Weeks 16 and 48
	Safety and tolerability	Safety and tolerability evaluated by the incidence, severity and relationship to CC-93538 of adverse events (AEs), serious adverse events (SAEs), clinical laboratory abnormalities, changes in vital signs, physical examination abnormalities and the presence of anti-drug antibodies, including neutralizing antibodies when warranted	Through Week 48
Secondary	Eosinophil histologic response	Changes in mean number of peak eos per hpf in GI biopsies from baseline to Week 48	Week 48
	Eosinophil histologic response	Percent changes in mean number of peak eos per hpf in GI biopsies from baseline	Weeks 16 and 48
	Eosinophil histologic response (> 75% reduction)	The proportion of subjects achieving eosinophilic histologic response defined as a > 75% reduction of peak gastric and/or duodenal eos count from baseline, respectively	Weeks 16 and 48

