#### **6.4.2.10 *Worsening of EGE Symptoms, EGE Flare, and the EGE Flare Assessment Visit***

Subjects with a worsening of EGE symptoms during the study, either in the Induction Phase, Maintenance Phase, or the OLE Phase will be required to complete the EGE Flare Assessment Visit as shown in the Table of Events ([Table 4](#), [Table 5](#), and [Table 6](#)). Subjects with increased signs and symptoms of EGE are instructed to contact the investigator and/or study staff to determine if an EGE Flare Assessment Visit is warranted.

- Worsening of EGE symptoms is defined as continuous worsening of symptoms for 2 consecutive visits (4 weeks apart) compared to baseline, measured by the weekly Izumo Scale score ( $\geq$  4 weeks of no change from baseline or  $\geq$  4 weeks of worsening from baseline).

An EGE Flare Assessment Visit including safety and efficacy evaluations can occur at any time during the study. An EGD may be required at the EGE Flare Assessment Visit to determine if use of rescue therapy is clinically indicated. Alternatively, if endoscopy is conducted as an intervention during an emergency department visit or hospitalization for a worsening of EGE symptoms or flare, medical record source data including details of the endoscopic procedure should be collected for the EGE Flare Assessment Visit EGD requirement. In addition, all attempts should be made to collect biopsy samples, and these samples should be sent to the central reader for histologic analysis. The results of the centrally read gastric/duodenal eos count will be blinded to investigative sites with the exception of screening during the Induction Phase and the Maintenance Phase. If the results of the gastric/duodenal eos count are required to determine the need for emergent rescue therapy, the results of the gastric/duodenal eos count will be disclosed as long as the investigator requires the result. If the results of the gastric/duodenal eos count will be disclosed in the Induction Phase, the subject is to be discontinued from the study and will not be allowed to enter either the Maintenance Phase or the OLE Phase. (See [Section 3.1.6](#).)

The investigator will confirm if the worsening of EGE symptoms requires rescue therapy and, thus, is deemed a severe EGE flare according to the following protocol definitions.

Any worsening of EGE symptoms during study participation will be documented as an EGE flare.

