## **9.7 Safety Analysis**

Safety analysis will be performed for the Induction Phase and by treatment and in total CC-93538 for the Maintenance Phase. The assessment of safety will include AEs, SAEs, AEs leading to discontinuation of study treatment, changes from baseline in laboratory values and vital signs, and incidence and type of laboratory, vital signs, and physical examination abnormalities. Safety data

will be summarized by treatment group using descriptive statistics. Individual data listings will also be provided.

Adverse events will be monitored during the study, and the data will be analyzed with respect to incidence within each treatment group as well as severity and potential relationship of the AEs to IP.

Laboratory assessments will be performed by a central laboratory. All summaries will be based on the standard International System of Units (SI) provided by the central laboratory. Each subject's hematology, blood chemistry, and urinalysis values will be flagged as "low", "normal", or "high" relative to the normal ranges of the central laboratory.

Summary statistics of actual values and changes from baseline in vital signs will be provided by visit.

Overall safety and tolerability will be summarized for each drug presentation (the 360 mg dose of CC-93538 administered by two injections of 1.2 mL each at a concentration of 150 mg/mL CC-93538 or by one injection of 2.0 mL at a concentration of 180 mg/mL CC-93538 administered with the PFS device constituent part or by one injection of 2 mL at a concentration of 180 mg/mL CC-93538 administered with the [REDACTED] device constituent part) utilizing descriptive statistics.

[figure not shown]

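### Section 10.1 excludes non-serious EGE flare symptoms from adverse events, yet requires drug toxicity to be reported as one, and does not say which rule governs a flare symptom suspected of being drug-related

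*Combined protocol and SAP*

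**What the plan says.** - **Section 10.1, first paragraph.** The definition is broad: "An AE is any noxious, unintended, or untoward medical occurrence that may appear or worsen in a subject during the course of a study", whatever the cause. The paragraph then turns to worsening, meaning "any clinically significant adverse change in the frequency or intensity of a pre-existing condition", which "should be considered an AE except for symptoms associated with an EGE flare requiring an EGE Flare Assessment". The one stated exception to that exclusion is a flare that meets a seriousness criterion. It is recorded both as an SAE and as a flare.
- **Section 10.1, second paragraph.** "Abuse, withdrawal, sensitivity or toxicity to an IP should be reported as an AE". This sentence sets no seriousness threshold and does not mention flares.
- **Section 6.4.2.10** (repeated in Sections 3.1.6 and 6.2.1). "Any worsening of EGE symptoms during study participation will be documented as an EGE flare".
- **Sections 10.2 and 10.2.3.** Severity and causality are assessed for AEs and SAEs. Causality is binary, and a reasonable possibility that IP caused the event is enough for the event to count as suspected.
- **Section 9.7.** "The assessment of safety will include AEs, SAEs, AEs leading to discontinuation of study treatment", with laboratory, vital-sign and physical examination findings. Flares are not listed. They are also absent from the internal safety team's review list in Section 9.9.3.
- **Table 2.** The key secondary safety endpoint reads "Safety and tolerability evaluated by the incidence, severity and relationship to CC-93538 of adverse events (AEs" and continues with SAEs, laboratory findings and so on. Time to EGE flare through Week 48 is a separate secondary endpoint. Section 9.6.3.1 analyses it as time to first event, with Kaplan-Meier estimates and a stratified log-rank test.

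**The concern.** The symptoms of EGE in Section 1.1.2 (abdominal pain, nausea, vomiting, poor appetite, bloating, diarrhea) are also what a non-specific gastrointestinal drug reaction would look like. When disease and possible drug effect share a symptom set, the rule separating disease worsening from an adverse event decides what reaches the safety tables.

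Here that rule points two ways. If an investigator follows the flare exclusion, a symptom suspected of being caused by IP leaves no severity grade and no causality record. The key secondary safety endpoint is built on incidence, severity and relationship to CC-93538, so such an event contributes to none of the three. If another investigator follows the toxicity sentence, the same event is counted. Recording could then differ between sites for a reason unrelated to treatment.

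**Working it through.** The point turns on text, and the plan gives no figure to reproduce. I followed one event through the rules: a blinded investigator sees a non-serious increase in diarrhea on treatment and thinks there is a reasonable possibility that IP caused it.

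1. **Is it a flare?** The broad sentence in Section 6.4.2.10 makes any worsening a flare, without asking about cause. The same section also defines worsening more narrowly, as continuous over two consecutive visits four weeks apart. The boundary is therefore loose.
2. **Is it an AE?** The flare exclusion says no. The general definition and the toxicity sentence point to yes. The section states no precedence, and the exclusion is the more specific instruction.
3. **Does the flare visit settle it?** AEs are assessed at that visit (Section 6.2.1), but under the same Section 10.1 definition. No section asks for a causality judgement on a non-serious flare.
4. **Does the seriousness route catch it?** Only in part. Section 6.4.2.10 grades a flare severe by the need for rescue therapy. Section 10.2.1 does not treat emergency outpatient care without admission as serious unless another criterion is met. A severe flare need not be an SAE.

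Sorting the possible events:

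| Event | Result under Section 10.1 |
|---|---|
| Flare meeting a seriousness criterion | SAE and flare |
| New occurrence that is not EGE worsening | AE |
| Symptom established as IP toxicity | AE, by the toxicity sentence |
| Non-serious flare symptom, drug cause suspected only | Unresolved; can be flare only |
| Non-serious flare symptom, drug cause not recognised | Flare only |

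**Size.** The documents give neither a gastrointestinal event rate in EGE nor the share of events that would be filed only as flares. The nearest figure is in Section 1.2.2.5: one subject with drug-related frequent bowel movements among 52 healthy adults given a single dose, 1/52 = 1.9%. That shows such an event is plausible and gives no rate for this trial.

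To show direction only, let p1 and p0 be the true rates of gastrointestinal events on drug and placebo, and let f be the fraction filed only as flares, taken as equal in both arms. All three are assumptions. The risk difference left in the AE table is (p1 − p0) × (1 − f).

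| p1 v p0 | f = 0 | f = 25% | f = 50% | f = 75% |
|---|---|---|---|---|
| 30% v 10% | 20 points | 15 | 10 | 5 |
| 40% v 15% | 25 points | 18.8 | 12.5 | 6.2 |

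**The case against.** The strongest reply is that the missing safeguard is already there: toxicity to IP is to be reported as an AE, with no exemption for flares. The exclusion is also narrow. It sits in the sentence on worsening of a pre-existing condition, so new occurrences stay AEs, and it applies only to flares that require a Flare Assessment. Flares stay visible by arm through the time-to-flare analysis, and the Izumo diarrhea and gastric pain domains are compared by arm as well. Section 9.1 defers detail to a SAP and Section 9.9.4 defers the DMC's data to a charter. The text of neither is in the documents reviewed, so a flare table may be planned there.

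Much of this stands, and it rules out several stronger readings that a reader might infer:

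- *There is no exception for drug-caused symptoms, so all non-serious gastrointestinal toxicity is lost.* The toxicity sentence contradicts this.
- *The trial cannot show such toxicity.* An excess of flares on drug would still appear in a randomized comparison through Week 48.
- *Half of drug-related events would be of this kind*, because one of the two subjects with a drug-related event in the Phase 1 study had a bowel event. Two subjects cannot support a rate.
- *The gap is widest in the open-label extension.* Most of Table 3 is unreadable, so its flare endpoints are unknown, and that phase has no comparator.

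The reply does not close the gap for suspected events. The toxicity sentence does not use the suspected threshold of Section 10.2.3 and does not say that it overrides the exclusion. The time-to-flare analysis is also a poor stand-in for a safety table. It counts first events and carries no causality. The worsening definition also covers four weeks or more of no change from baseline, so lack of response counts as a flare, and a benefit of the drug could offset worsening that it causes.

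**Conclusion.** The point holds as an unreconciled pair of rules in Section 10.1. A non-serious gastrointestinal flare symptom that is suspected, but not established, to be drug-related can be recorded as a flare alone and so drop out of the key secondary safety endpoint. Serious flares, clearly new events and recognised toxicity are not affected. The number of events at risk is unknown and cannot be estimated from the documents; the attenuation figures above rest wholly on assumed rates. The conclusion assumes that sites apply the flare exclusion as written and that no SAP or case report form instruction outside these documents already resolves the conflict.

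**What to change.** 1. **Section 10.1.** Reconcile the two rules with one clause: flare symptoms suspected of being related to IP, in the sense of Section 10.2.3, are recorded as an AE with severity and causality in addition to the flare. This extends the dual recording already used for serious flares.
2. **Section 9.7.** Add a descriptive table of EGE flares by arm and by phase, placed beside the gastrointestinal AEs. The clause cannot capture drug effects that a blinded investigator does not recognise; this table lets a reader see flares and gastrointestinal AEs together.

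The cost is one clause, the matching site instruction and one table. Some events will appear both as a flare and as an AE, so the table should be footnoted to say that the two counts overlap.

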## 10.2 Evaluation of Adverse Events

A qualified investigator will evaluate all AEs as to seriousness, severity/intensity, causality, duration, action taken, and outcome.

### 10.2.1 Seriousness

An SAE is any AE occurring at any dose that:

- Results in death;
- Is life-threatening (ie, in the opinion of the investigator, the subject is at immediate risk of death from the AE);
- Requires inpatient hospitalization or prolongation of existing hospitalization (hospitalization is defined as an inpatient admission, regardless of length of stay);
- Results in persistent or significant disability/incapacity (a substantial disruption of the subject's ability to conduct normal life functions);
- Is a congenital anomaly/birth defect;
- Constitutes an important medical event.

Important medical events are defined as those occurrences that may not be immediately life-threatening or result in death, hospitalization, or disability, but may jeopardize the subject or require medical or surgical intervention to prevent one of the other outcomes listed above. Medical and scientific judgment should be exercised in deciding whether such an AE should be considered serious.

Events **not considered** to be SAEs are hospitalizations for:

- routine treatment or monitoring of the studied indication not associated with any deterioration in condition.
- a procedure for protocol/disease-related investigations (eg, surgery, scans, EGD, sampling for laboratory tests, bone marrow sampling). However, hospitalization or prolonged hospitalization for a complication of such procedures remains a reportable SAE.
- hospitalization or prolongation of hospitalization for technical, practical, or social reasons, in absence of an AE.
- a procedure that is planned (ie, planned prior to start of treatment on study); must be documented in the source document and the eCRF. Hospitalization or prolonged hospitalization for a complication remains a reportable SAE.
- an elective treatment of or an elective procedure for a pre-existing condition, unrelated to the studied indication, that has not worsened from baseline.
- emergency outpatient treatment or observation that does not result in admission, unless fulfilling other seriousness criteria above.

If an AE is considered serious, the AE screen of the eCRF must be completed and ticked “serious”.

For each AE, the investigator will provide information on severity, start and stop dates, relationship to the IP, action taken regarding the IP, and outcome.

### **10.2.2 Severity/Intensity**

For both AEs and SAEs, the investigator must assess the severity/ intensity of the event.

